7.2 Statistical Methods

We have performed within subject comparisons and measurements on PBMC and biopsy using appropriate paired analysis (paired t-test or equivalent nonparametric test (Wilcoxon Signed Rank test) (12, 13). Repeated measures of analysis of variance (RM-ANOVA) were used to test the trajectory variations over time. Two-sided F-test statistics were applied using $\alpha=0.05$. For proteogenomic bioinformatics analysis, we have reported for each gene/protein comparison the T-test p-value, its non-parametric analog (Kruskal Wallis test), the fold change, and for multi-analyte signatures, the AUROC curve (C-index) and the q-values by member genes/proteins. We were then able to calculate the predictive accuracy, sensitivity and specificity of each signature. For clinical endpoints, categorical and continuous variables will be analyzed with appropriate tests (Fisher's exact, T-test). $P<0.05$ will be considered significant

7.3 *Subject Population(s) for Analysis*

All subjects (successful vs. failed, withdrawn from the study vs. maintained) will be followed and analyzed at study end. We will also document the number of patients screened who did not meet I/E criteria at the study initiation.

8 Safety and Adverse Events

8.1 *Definitions*

Adverse Event

By definition an **adverse event** (AE) is defined as: any symptom, sign, illness or experience that develops or worsens in severity during the course of the study. Intercurrent illnesses or injuries should be regarded as adverse events. Abnormal results of diagnostic procedures are considered to be adverse events if the abnormality:

- results in study withdrawal
- is associated with a serious adverse event
- is associated with clinical signs or symptoms
- leads to additional treatment or to further diagnostic tests
- is considered by the investigator to be of clinical significance

Adverse events are classified as serious or non-serious.

Serious Adverse Event

. A **serious adverse event** is any AE that is:

- fatal
- life-threatening
- requires or prolongs hospital stay
- results in persistent or significant disability or incapacity
- a congenital anomaly or birth defect
- an important medical event

Events that are expected, anticipated, related to the standard of care treatment or known adverse events/serious adverse events from standard of care medications or pre-existing conditions will not be reported.

Important medical events are those that may not be immediately life threatening, but are clearly of major clinical significance. They may jeopardize the subject, and may require intervention to prevent one of the other serious outcomes noted above. For example, drug overdose or abuse, a seizure that did not result in in-patient hospitalization, or intensive treatment of bronchospasm in an emergency department would typically be considered serious.

All adverse events that do not meet any of the criteria for serious will be regarded as **non-serious adverse events**.

Adverse Event Reporting Period

For the purposes of this study, Adverse events and Serious Adverse events will be defined as those that are related to the procedures performed specifically for the study which are:

liver biopsy (regardless if performed percutaneously, transjugularly or open) and phlebotomy which takes place only to draw study-related blood. The study period during which adverse events must be reported is normally defined as the period from the initiation of any study procedures to the end of the study treatment follow-up. For this study, the study treatment follow-up the last visit made for the study.

Preexisting Condition

A preexisting condition is one that is present at the start of the study. The pre-existing conditions will be recorded prior to the start of the study. A preexisting condition should be recorded as an adverse event if the frequency, intensity, or the character of the condition worsens during the study period.

General Physical Examination Findings

At screening, any clinically significant abnormality should be recorded as a preexisting condition. At the end of the study, any new clinically significant findings/abnormalities that meet the definition of an adverse event must also be recorded and documented as an adverse event.

Post-study Adverse Event

All unresolved adverse events should be followed by the investigator until the events are resolved, the subject is lost to follow-up, or the adverse event is otherwise explained. At the last scheduled visit, the investigator should instruct each subject to report any subsequent event(s) that the subject, or the subject's personal physician, believes might reasonably be related to participation in this study. The investigator should notify the study sponsor of any death or adverse event occurring at any time after a subject has discontinued or terminated study participation that may reasonably be related to this study. The sponsor should also be notified if the investigator should become aware of the development of cancer or of a congenital anomaly in a subsequently conceived offspring of a subject that has participated in this study.

Abnormal Laboratory Values

A clinical laboratory abnormality should be documented as an adverse event if any one of the following conditions is met:

- The laboratory abnormality is not otherwise refuted by a repeat test to confirm the abnormality
- The abnormality suggests a disease and/or organ toxicity
- The abnormality is of a degree that requires active management; e.g. change of dose, discontinuation of the drug, more frequent follow-up assessments, further diagnostic investigation, etc.

Hospitalization, Prolonged Hospitalization or Surgery

Any adverse event that results in hospitalization or prolonged hospitalization should be documented and reported as a serious adverse event unless specifically instructed otherwise in this protocol. Any condition responsible for surgery should be documented as an adverse event if the condition meets the criteria for an adverse event.

Neither the condition, hospitalization, prolonged hospitalization, nor surgery are reported as an adverse event in the following circumstances:

- Hospitalization or prolonged hospitalization for diagnostic or elective surgical procedures for a preexisting condition. Surgery should **not** be reported as an outcome of an adverse event if the purpose of the surgery was elective or diagnostic and the outcome was uneventful.
- Hospitalization or prolonged hospitalization required to allow efficacy measurement for the study.
- Hospitalization or prolonged hospitalization for therapy of the target disease of the study, unless it is a worsening or increase in frequency of hospital admissions as judged by the clinical investigator.

8.2 Recording of Adverse Events

At each contact with the subject, the investigator/designee must seek information on adverse events by specific questioning and, as appropriate, by examination. All clearly related signs, symptoms, and abnormal diagnostic procedures results should be recorded in the source document, though should be grouped under one diagnosis.

All adverse events occurring during the study period must be recorded. The clinical course of each event should be followed until resolution, stabilization, or until it has been determined that the study treatment or participation is not the cause. Serious adverse events that are still ongoing at the end of the study period must be followed up to determine the final outcome. Any serious adverse event that occurs after the study period and is considered to be possibly related to the study treatment or study participation should be recorded and reported immediately.

8.3 Reporting of Serious Adverse Events

8.3.1 EC/IRB Notification by Investigator

Reports of all serious adverse events (including follow-up information) must be submitted to the Northwestern University Institutional Review Board (NUIRB) within 10 working days. Copies of each report and documentation of NUIRB notification and receipt will be kept in the Clinical Investigator's binder.

8.4 Stopping Rules

If any of the following criteria are met, study enrollment will be suspended and participants will be maintained on their current IS therapy or may be required to restart IS therapy: 1) Rejection induced by IS weaning resulting in death, retransplantation or listing for retransplantation in any one subject; 2) Either steroid-resistant rejection or chronic rejection occurring during weaning in >10% of subjects (2 patients)

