11.3	SUBJECT STIPENDS OR PAYMENTS	1748
13	PUBLICATION PLAN.....	1748
14	REFERENCES.....	1849

List of Abbreviations

AE	Adverse Event
ALK Phos	Alkaline Phosphatase
ALT	Alanine Aminotrasferase
AST	Aspartate Transaminase
AUROC	Area Under Receiver Operating Characteristic (Curve)
CBC	Complete Blood Count
CKD	Chronic Kidney Disease
CMP	Comprehensive Metabolic Panel
CNI	Calcineurin Inhibitor
CRF	Case Report Form
Cr	Creatinine
CTC	Comprehensive Transplant Center
eCRF	Electronic Case Report Form
eGFR	Estimated Glomerular Filtration Rate
FDA	Food and Drug Administration
GCP	Good Clinical Practice
GFR	Glomerular Filtration Rate
GGT	Gamma-Glutamyl Transpeptidase
HBV	Hepatitis B Virus
HCV	Hepatitis C Virus
HbA1C	Hemoglobin
HIPAA	Health Insurance Portability and Accountability Act of 1996
HIV	Human Immune Deficiency Virus

I/E	Inclusion/Exclusion
ICH	International Conference on Harmonization
IHC	Immunohistochemical
IL-2	Interleukin 2
IM	Immune Monitoring
IRB	Institutional Review Board
IS	Immunosuppression
ITN	Immune Tolerance Network
LFT	Liver Function Tests
LT	Liver Transplant
MDRD-4	Modification of Diet in Renal Disease-4 (version four)
MLR	Mixed Lymphocyte Reaction
NIAID	National Institute of Allergy and Infectious Disease
NIH	National Institutes of Health
NUIRB	Northwestern University Institutional Review Board
OLT	Orthotopic Liver Transplant
PBMC	Peripheral Blood Mononuclear Cell
PI	Principal Investigator
pLTQ	Post Liver Transplantation Quality of Life Instrument
PTLD	Post Transplant Lymphoproliferative Disorder
QOL	Quality of Life
RM-ANOVA	Repeated Measures o fAnalysis of Variance
SAE	Serious Adverse Event
SRL	Sirolimus

TAC Tacrolimus

ULN Upper Limit of Normal

Study Summary

Title	Liver Transplant Tolerance Enhanced By Sirolimus Therapy
Short Title	Sirolimus-Enhanced Tolerance
NU Protocol Number	STU00071766
Phase	Phase 4, pilot study
Methodology	Open label prospective study of Sirolimus withdrawal
Study Duration	18 months
Study Center(s)	Single-center
Objectives	Objectives: 1. To determine if tolerance can be achieved successfully in a reasonable percentage (>20%) of liver transplant (LT) recipients withdrawn from SRL monotherapy. 2. To investigate if blood/allograft metrics of immunoregulation correlate with successful SRL withdrawal in LT recipients.
Number of Subjects	25 Subjects meeting inclusion/exclusion criteria

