3.1 General Design

Study Overview

The study proposed is a prospective trial of controlled SRL monotherapy minimization and withdrawal in up to 25 stable non-immune non-viremic LT recipients. Given the sample size calculations (see Statistical section), we plan to enroll up to 25 SRL monotherapy patients for this study (Figure 1). All patients will be consented to undergo laboratory evaluation as well as an enrollment liver biopsy and blood tests. If the patient meets inclusion/exclusion (I/E) criteria (see below), SRL will be minimized over 6 months until once a week dosing is achieved. Repeat clinical and immunological blood tests as above will be performed, and if no biochemical signs of rejection, SRL will be discontinued with blood tests and liver biopsy 12 months later for similar biochemical, histological and immunological measures. At any concern for rejection, liver biopsy and assays for equivalent biochemical, histological and immunological measures will be performed and if rejection is diagnosed on biopsy, a second attempt at withdrawal **will not** be performed. Patients will be monitored as standard of care with clinic visits every 6 months and laboratory tests every 2 weeks. The total study length will be 18 months: 6 month minimization phase and 1 year follow-up after withdrawal success/failure. The primary outcome will be the proportion of tolerant patients off SRL therapy with normal liver biochemistry and graft histology at 18 months. Secondary outcomes will include the incidence, severity and reversibility of rejection, patient/graft survival, resolution of SRL and other non-specific IS effects, and the assessment of clinical/immunological biomarkers of tolerance. All continuous/categorical clinical variables will be compared with the appropriate statistical analyses. The goal is that the primary and secondary aims will provide valuable preliminary data to further elucidate the mechanisms of mTOR-I immunoregulation and for determining the initial clinical success/feasibility of the mTOR-I approach (vs. historical 20% CNI withdrawal success seen in studies from the Immune Tolerance Network [ITN] and other groups). This is all so as to guide a submission to the Immune Tolerance Network for larger, more adequately powered prospective trials comparing SRL vs. CNI withdrawal and accompanying biomarker predictors of tolerance. If this pilot study fails to show a correlation between our biomarkers and the success/failure of SRL withdrawal, or is associated with an unacceptable low (e.g. <20%) rate of operational tolerance, then this would avoid the necessity for such large, expensive trials and support the continued development of alternative approaches to tolerance.

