
Consent and Initial Phase of Enrollment (see Study Protocol Figure- Appendix A)

These liver transplant candidates (up to 25 SRL) will be approached for consideration and informed consent into the study. The consent form will include discussion of the risks/benefits of their current therapy (SRL) and the planned minimization/withdrawal. Specifically, the risks of minimization/withdrawal (i.e. developing acute or chronic rejection, alloimmune hepatitis during any portion of the study), although unlikely, will be a major emphasis of the consent process. The consent form will also include the strict requirement for patients to follow all instructions from the PI in regard to the close laboratory follow-up occurring throughout the trial, to diagnose any episode of rejection or concern as early as possible to be able to respond appropriately. All of the study procedures will be discussed with the patient during clinic visits. They will be informed that neither participation nor refusal will influence their clinical care. All laboratory tests or costs related to their care in the study, with the exception of non-standard of care items (i.e. liver biopsies, blood assays), will be the responsibility of the

patient and/or his/her insurance company. They will be asked questions afterwards to verify comprehension and then sign the consent form documenting their agreement to participate. A signed copy of the consent form will be given to them. Participation is completely voluntary and they may discontinue participation the study at any time without affecting their care or participation in any other study. No financial compensation will be given.

Screening Evaluation at Enrollment (see Study Protocol Figure)

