After long term (> 3 years post-LT, > 3 months on SRL monotherapy) on SRL monotherapy, inclusion/exclusion criteria will be reviewed and if appropriate, consent as above will be obtained. If the patient agrees and signs consent, baseline standard of care screening laboratories complete blood count, comprehensive metabolic panel, sirolimus (CBC, CMP, SRL trough level, fasting lipid profile, hemoglobin A1C [HbA1C], urine protein/creatinine ratio) and non-standard of care biomarker assays (blood immunophenotyping, proteogenomics) and liver biopsy (histology and graft immunohistochemistry) will be performed as dictated by the protocol. In addition, the liver biopsy will be used to determine stability in graft function (i.e. no evidence of rejection or immune-mediated hepatitis) before considering minimization/withdrawal. SRL minimization/withdrawal will only be performed if clinically, biochemically and histologically [by biopsy; liver transplant pathology read ([name], [name])] stable. Throughout the entire study, liver function tests will be monitored every 2 weeks (monthly is standard of care, so the interim non-standard of care 2 week blood tests will be covered by the study funds). Patients entering the minimization/withdrawal phases will be reduced by a total dose of 50% of their baseline dose every month until patients are on 0.5 mg SRL daily. At this point, every other day dosing will begin x 1 month. If no LFT abnormalities, twice weekly dosing x 1 month, then once a week dosing x 1 month. Prior to complete discontinuation, repeat clinical (screening labs above) and blood biomarker assays (blood immunophenotyping, proteogenomics) will be performed. Liver biopsy will not be performed at this juncture unless there are biochemical signs of liver injury. If complete withdrawal is deemed safe (no evidence of biochemical abnormalities) patients will be withdrawn completely (i.e. the once/week SRL dose discontinued) and followed off IS therapy for one year. In this time period, liver function tests will be monitored every 2 weeks, as usual, and repeat clinical (screening labs above), liver biopsy and blood (blood immunophenotyping, proteogenomics) assays performed at the end of this year or at any concern for rejection.

Blood and Tissue Samples

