any patient throughout the study developing liver dysfunction (direct bilirubin >1 mg/dL; ALT, AST, or AlkPhos > 2xULN), this will be confirmed on a repeat blood test within 1-2 weeks and if persistent, liver biopsy will be performed. Immediately before complete withdrawal, i.e. repeat clinical (screening labs) and blood assays will be performed. If complete withdrawal is deemed safe (no evidence of biochemical abnormalities, i.e. direct bilirubin < 1 mg/dL; ALT, AST, or AlkPhos < 2xULN), patients will be withdrawn completely (i.e. the once/week SRL dose discontinued) and followed off SRL therapy for one year. In this time period, liver function tests will be monitored every 2 weeks. At 12 months following withdrawal, the same history and physical, QOL survey, screening labs and blood IM assays will be performed as in the study initiation, as well as the liver biopsy- all for the primary endpoint. If rejection or immune-mediated hepatitis is seen on this post-withdrawal biopsy or at any time during the study period, the patient will be reinitiated on IS therapy appropriately per the PI and not have another withdrawal attempt. All patients will be followed until 1 year post-attempted withdrawal, even if unsuccessful, although patients developing rejection or resumption of IS prior to this period will not have a final liver biopsy performed (i.e. only those presumed tolerant or who did not have rejection).

Blood and Tissue Samples

Standard of care laboratories complete blood count, liver function tests (CBC, LFTs) will be performed every 2 weeks on all patients. Please see Figure 1 above for sample collections. A separate clinical informed consent will be obtained each time a liver biopsy is performed. If the patient develops elevation in liver transaminases requiring a liver biopsy at any stage of the minimization/withdrawal phase, blood assays will be requested from the patient at the time of the biopsy. These immunological data in rejecting patients will be important to compare to patients who successfully are minimized and withdrawn.

Follow-up

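### Stopping rule 2 equates more than 10% of subjects with 2 patients, but 2 of the planned 25 is 8%; the percentage is first exceeded at 3, and no denominator is defined

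*Combined protocol and SAP*

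**What the plan says.** Section 8.4 gives two stopping criteria. The first is triggered by a single subject whose rejection leads to death, retransplantation or listing. The second is "Either steroid-resistant rejection or chronic rejection occurring during weaning in >10% of subjects (2 patients". When either is met, enrollment is suspended, and participants stay on their current immunosuppression or may have to restart it.

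The Study Summary gives the sample size as "25 Subjects meeting inclusion/exclusion criteria". Section 3.1 makes 25 a maximum, describing "controlled SRL monotherapy minimization and withdrawal in up to 25 stable non-immune non-viremic LT recipients". No section says whether the percentage in rule 2 refers to subjects planned, enrolled, started on dose reduction or treated to date, or whether the percentage or the count prevails.

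On timing, section 3.1 describes a "6 month minimization phase and 1 year follow-up after withdrawal success/failure". Section 4.3 says "patients will be withdrawn completely (i.e. the once/week SRL dose discontinued) and followed off SRL therapy for one year". The consent text in section 3.1 warns of "developing acute or chronic rejection, alloimmune hepatitis during any portion of the study". Rule 2 is limited to events during weaning, a word that appears only in section 8.4 and is not defined there.

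**The concern.** A stopping rule has to give one answer when the event occurs. Rule 2 states its threshold twice, and at the planned size the two statements disagree. The disagreement falls on the second event, which is the event the printed count names.

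The rule reaches beyond enrollment: once met, it also governs whether patients already tapering or off drug continue. It is the only preset numerical trigger for severe rejection short of death, retransplantation or listing. Under section 8.5 the Principal Investigator oversees safety, and the documents name no independent monitoring committee to settle the ambiguity. Section 1.4 also cautions that the reversibility seen in withdrawal studies done mainly with calcineurin inhibitors may not carry over to sirolimus. Steroid-resistant and chronic rejection are the events that would show this.

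A secondary point concerns wording. If weaning means only the dose-reduction phase, events in the following year off drug would not count toward rule 2. If it includes that year, they would. The text supports either reading.

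**Working it through.** **Inputs.** Percentage threshold: strictly more than 10% (section 8.4). Count: 2 patients (section 8.4). Planned size: 25 (Study Summary), a maximum in section 3.1.

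**Step 1: try to reproduce the plan's figure at 25.** 10% of 25 is 2.5, so the smallest whole number above it is 3.

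- 2/25 = 8.0%, which does not exceed 10%.
- 3/25 = 12.0%, which does.

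The printed 2 is not reproduced. Reading the threshold as at least 10% still requires 3 at 25. A denominator of 20 with that looser reading would give 2 (2/20 = 10.0%), but the only 20 near this topic is in section 7.1, where it describes earlier biomarker studies and not this trial's size.

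**Step 2: find where the count and the percentage agree.** The smallest count r with r/n > 0.10 is floor(n/10) + 1.

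| Denominator n | Smallest count above 10% | Boundary check | Agrees with 2 patients? |
|---|---|---|---|
| 1 to 9 | 1 | 1/9 = 11.1% | No: the percentage triggers earlier |
| 10 to 19 | 2 | 1/10 = 10.0%; 2/19 = 10.5% | Yes |
| 20 to 25 | 3 | 2/20 = 10.0%; 2/25 = 8.0%; 3/25 = 12.0% | No: the percentage triggers later |

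The first row matters only if the denominator is a running total. The text neither states nor excludes that.

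**Step 3: size of the difference.** The documents give no expected rate for steroid-resistant or chronic rejection, so the true rate p is assumed over a range. With all 25 exposed for the full period and X binomial(25, p):

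- P(X ≥ 2) = 1 − (1−p)^25 − 25p(1−p)^24
- P(X ≥ 3) = P(X ≥ 2) − 300p²(1−p)^23, where 300 = 25 × 24 / 2

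| Assumed p | P(X ≥ 2) | P(X ≥ 3) | P(exactly 2), by subtraction |
|---|---|---|---|
| 1% | 0.0258 | 0.0020 | 0.0238 |
| 2% | 0.0886 | 0.0132 | 0.0754 |
| 5% | 0.3576 | 0.1271 | 0.2305 |
| 10% | 0.7288 | 0.4629 | 0.2659 |

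The last column is the chance that the study ends with exactly two events, so that the two halves of the rule give different answers for the final total of 25. These are end-of-study probabilities. They do not show how often a trigger would come early enough to suspend enrollment.

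**The case against.** The strongest reply is that the rule prints an integer. Anyone who follows it has a clear trigger, and at 20 to 25 subjects it is the more cautious one. Harm would require someone to set the printed count aside in favor of the percentage. Other protections do not depend on rule 2: a patient with rejection goes back on immunosuppression without a second attempt, liver tests are scheduled every two weeks, the IRB can stop the study, and rule 1 needs only one subject. Because 25 is a ceiling, final enrollment of 10 to 19 would make the discrepancy disappear.

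Part of this stands. The printed count is not unsafe, and the mismatch depends on the denominator. The other protections, however, act on individual patients, at the IRB's discretion, or only on the outcomes in rule 1. They do not replace a clear study-level trigger. Nothing in section 8.4 gives the count precedence. As the sentence is built, the percentage is the criterion and the count explains it. The argument from a smaller denominator also concedes that the denominator is undefined.

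The assumed event rates are a fair target too. The nearest figures, in sections 1.3 and 1.4, point low: graft failure below 1%, and a single patient in the major withdrawal studies with chronic rejection needing retransplantation. Those data come mainly from calcineurin inhibitor withdrawal and describe different events, but no section supports the 5% and 10% rows. At 1% the contrast is small in absolute terms. The inconsistency does not depend on the rate.

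On weaning, section 3.4 already makes rejection with withdrawal, and graft function to the end of the study, safety endpoints. Later events are therefore monitored; only their counting toward rule 2 is unclear. Whether they should count is a design decision.

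**Conclusion.** The concern holds. At the planned 25 subjects, and at any denominator from 20 to 25, rule 2 gives two different answers at the second event: stop by the count, continue by the percentage. This is an incorrect threshold in a safety rule and should be corrected. It is not evidence that the printed count is unsafe, and neither rule 1 nor any efficacy estimate is affected.

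The arithmetic requires no assumption beyond the denominator. Its practical size does: with 25 fully exposed patients, the probability of ending with exactly two events runs from about 2% at a 1% event rate to about 27% at a 10% rate, all at assumed rates. The undefined scope of weaning is a lesser, separate ambiguity in the same sentence.

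**What to change.** Amend rule 2 in section 8.4 to state one integer trigger. The simplest choice is 2 or more patients with steroid-resistant or chronic rejection, with the percentage removed. This keeps the stricter printed count and stays correct if fewer than 25 enroll. If a percentage is wanted, state its denominator, for example subjects who have started sirolimus minimization, and make the two match: 2 of 25 is 8%, and 3 of 25 is the first count above 10%. The choice between 2 and 3 belongs to the sponsor and the IRB.

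In the same sentence, replace the reference to weaning with an explicit period. I would count events from the first dose reduction through the end of the year off drug, since patients remain at risk then, but this too is for the sponsor and the IRB to decide.

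The cost is one sentence by amendment, with no new data, visits or analyses.
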